6.1 Baseline Values

Unless otherwise noted, baseline is defined as the last nonmissing value recorded prior to the first administration of the trial product. Unscheduled visits will be used for the determination of baseline values, when applicable.

6.2 Adjustments for Covariates

Not applicable

6.3 Handling of Dropouts or Missing Data

Summaries will be based on a valid case basis, ie, on observed data only, unless specified otherwise.

Missing or incomplete dates of (unsolicited) AEs will be imputed to assess whether an AE occurred prior to or after the first vaccination dose. Imputed dates are only further used for classification, but no other calculation like durations will be done. Imputation will also be considered for missing or incomplete CMs dates to determine whether a CM is prior, concomitant or ongoing.

The most conservative approach will be systematically considered. If the AE onset date is missing/incomplete, it is assumed to have occurred during the trial vaccination phase (ie, considered a post-vaccination AE) except if the partial onset date or other data, such as the end date, indicate differently.

The following algorithms will be applied to missing and incomplete AE start and stop dates:

Start Dates

- If the day portion of the start date is missing, then the start date will be estimated to be equal to the date of first administration of trial product, provided the start month and year are the same as the administration of trial product and the stop date is either after the first administration of trial product or completely missing. Otherwise, the missing day portion will be estimated as “15.”
- If both the day and month portions of the start date are missing, then the start date will be estimated to be equal to the date of first administration of trial product, provided the start year is the same as the first administration of trial product and the stop date is either after the first administration of trial product or completely missing. Otherwise, if the start year is lower than the year of first administration of the trial product, the event will be assumed to start on the mid-year point of the given year (eg, ??-??-2013 is estimated as 01-JUL-2013).
- If the start year is after the year of first administration of the trial product, the start date will be estimated as the first day of the year (ie, 01-JAN-YYYY).
- If the start date is completely missing and the stop date is either after the first administration of trial product or completely missing, the start date will be estimated to be the day of first administration of trial product. Otherwise, the start date will be estimated to be the first day of the same year as the stop date.

Stop Dates

- If only the day of resolution is unknown, the day will be assumed to be the last of the month (eg, ??-JAN-2013 will be treated as 31-JAN-2013) or at the date of last contact, if earlier.
- If both the day and month of resolution are unknown, the event will be assumed to have ceased on the last day of the year (eg, ??-??-2013 will be treated as 31-DEC-2013) or at the date of last contact, if earlier.
- If the stop date is completely missing or the event is continuing, the event will be assumed to be after the first administration of trial product and will be imputed using the date of last contact.

6.4 Interim Analysis and Data Monitoring

One or more interim analyses (IAs) may be performed for this trial. The data will be cleaned for all subjects. The analyses will be based on a data snapshot. Analyses will be performed on the safety set or subsets of it based on the availability of data. No decision-making is planned for the IAs and no adjustments for the trial are planned based on the results.

It is not planned to discuss any difference between the IAs and the final analysis in the clinical trial report.

A first interim analysis was performed after 16 subjects had been vaccinated (10 subjects in the CV7202 5 µg group and 6 subjects in the Rabipur group) and observed until Visit 8. The first interim analysis focused on safety aspects only. It was planned in a standalone interim analysis plan, which was finalized on 6 February 2019.

The second interim analysis was performed after 53 subjects had been vaccinated (16 subjects in the CV7202 1 µg group, 16 subjects in the CV7202 2 µg group, 10 subjects in the CV7202 5 µg group and 11 subjects in the Rabipur group) and observed until Visit 12 (Day 57). The second interim analysis focused on safety and immunogenicity. The analysis was primarily based on the interim analysis plan as of 06 February 2019 and subsequent change requests for tables.

For details of data monitoring please refer to section 4.

6.5 Examination of Subgroups

No subgroup analysis other than by dose regimen (treatment group) is planned.

6.6 Multiple Comparison/Multiplicity

No adjustments for multiple testing will be made in this trial.

6.7 Multicenter Studies

This is a multicenter trial with 2 sites in 2 countries participating in the trial.
No comparison of the results by trial site is planned.

7. NOTATION OF VACCINATION GROUPS AND VISITS

Notation of vaccination groups

The following notation of **vaccination groups** will be used throughout the report:

Full notation (as used in the trial protocol)	Notation as used throughout all tables, listings and figures
Group 3 
 • Group 3 without Group 3a • Group 3a 	CV7202 1 µg 
 • CV7202 1x1 µg • CV7202 2x1 µg
Group 4 
 • Group 4 without Group 4a • Group 4a 	CV7202 2 µg 
 • CV7202 1x2 µg • CV7202 2x2 µg
Group 2	CV7202 5 µg
Group 1	Rabipur

The administration of a second dose to every 8 of the 16 subjects in groups 3 and 4 was done in a sequential manner at the sites. Therefore this analysis does not differentiate between planned and actual vaccination group and done regimen and all analyses will be based on the actually received vaccination group and dose regimen.

Visit terminology

Visit	Notation as used throughout all tables, listings and figures¹
Visit 1 (Pre-screening Visit, Days -90 to -1)	V1 (Pre-screening)
Visit 2 (Screening Visit, Days -30 to -1)	V2 (Screening)
Visit 3 (Vaccination Dose 1 CV7202 or Rabipur, Day 1)	V3 (Day 1)
Visit 4 (Day 2 or 3*)	V4 (Day 2/3)
Phone call (Day 3)	Phone call 1 (Day 3)
Visit 5 (Vaccination Dose 2 Rabipur, Day 8)	V5 (Day 8)
Visit 6 (Day 10)	V6 (Day 10)
Visit 7 (Day 15)	V7 (Day 15)
Visit 8 (Vaccination Dose 2 CV7202 or Dose 3 Rabipur, Day 29)	V8 (Day 29)
Visit 9 (Day 30 or 31**)	V9 (Day 30/31)
Phone call (Day 31)	Phone call 2 (Day 31)
Visit 10 (Day 36)	V10 (Day 36)
Visit 11 (Day 43)	V11 (Day 43)
Visit 12 (Day 57)	V12 (Day 57)
Visit 13 (Day 91)	V13 (Day 91)
Visit 14 (Month 6: Day 181 [1-dose regimens]/ Day 209 [2-dose regimens and Group 1 {Rabipur}])	V14 (Month 6)
Optional Visit 14A***	V14A (M6+3)
Visit 15 (Month 12: Day 365 [1-dose regimens]/ Day 393 [2-dose regimens and Group 1 {Rabipur}])	V15 (Month 12)
Optional Visit 15A***	V15A (M12+3)
Visit 16 (Month 18: Day 547)	V16 (Month 18)
Optional Visit 16A***	V16A (M18+3)
Visit 17 (Trial End) (Month 24: Day 729)	V17 (Trial End/Month 24)
Optional Visit 17A***	V17A (M24+3)

* It should be noted that for subjects enrolled in the trial before Protocol Amendment 1 became effective, Visit 4 occurred on Day 3 as planned in the original protocol.

¹ Programming note: This visit notation should be applied in SDTM for the VISIT/VISITNUM variable. If VISIT is uppercased, then the preference is to assign a format to VISITNUM, display the formatted VISITNUM, order by the VISITNUM variable, and do not display VISIT.

** For some subjects already vaccinated with Rabipur before the last protocol amendment was issued, Visit 9 occurred on Day 31 as planned in the original protocol. For other subjects, the visit should occur on Day 30.

*** In case Visit 14, 15, 16, or 17 could not take place on site due to the public health emergency related to COVID-19, safety information should be collected via a phone call within the protocol-allowed time interval for that visit. In case Visit 14, 15, 16, or 17 was conducted as a phone call or not all procedures could be performed on site, Visits 14A, 15A, 16A, or 17A should be scheduled on site during a widened visit window starting the day after the expiry of the original visit window and lasting up to 3 months after the original projected visit date (+15-90 days).

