5.1.2 Stopping Rules

For dose escalation (group)

At each planned safety review, safety data will be reviewed and a GO/NO GO decision made accordingly for enrolment of further subjects and administration of subsequent doses.

Enrolment or administration at the given dose level will be temporarily halted and only continued after DSMB approval and approval by the competent authority following the occurrence of:

- Any related SAE in the opinion of the principal investigator (PI), the DSMB and/or the iSRC.
- Related severe AEs of the same kind in $\geq 20\%$ of the subjects in one group with the following exceptions:
 - Transient grade 3 chills, fatigue, headache, fever, myalgia or arthralgia resolving within 24 hours to grade ≤ 2 .
 - Transient grade 3 local AEs reducing to grade ≤ 2 within 48 hours.

Based on the review of the data, the DSMB will decide about temporary or permanent stopping of dosing in the given and eventually also lower dose groups (pertaining to the 2nd dose administration). After a temporary halt further measures for safety monitoring (i.e. additional safety visits including safety blood sampling at additional time points) may also be introduced based on DSMB recommendation.

For further CV7202 dose administration (subject)

Subjects must not receive a second dose of CV7202 in the event of:

- Occurrence of an allergic/anaphylactic reaction after the first dose.
- Any related SAE in the opinion of the PI, the DSMB and/or the iSRC.
- Any related severe (grade 3) AEs with the following exceptions:
 - Transient grade 3 chills, fatigue, headache, fever, myalgia or arthralgia resolving within 24 hours to grade ≤ 2 .
 - Transient grade 3 local reactions resolving to grade ≤ 2 within 48 hours.

If these reactions occur, the subject must not receive additional vaccinations but is encouraged to continue in trial participation for safety reasons, including collection of safety blood samples. Immunogenicity assessments may be performed at the investigator's discretion and if the subject agrees.

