5.2 Subject and Trial Completion

Subjects will be enrolled at pre-screening (Day -90 to -1) to receive either CV7202 starting Day 1 as 1 dose or 2 doses (at least 28 days apart), or 3 doses of control vaccine (Rabipur®). Follow-up for safety and immunogenicity is planned up to 24 months after the last dose, therefore the expected duration of participation for each subject is approximately 24 months after the last dose.

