8.4 Trial Groups

The subjects will be distributed among the different groups to receive CV7202 or Rabipur® (Table 8.1).

Table 8.1 Protocol CV-7202-104 Dose regimen

| | Trial Product | Composition | Dosing | | |
|--------------------------------|---------------|-------------|--------|-------|--------|
| | | | Day 1 | Day 8 | Day 29 |
| | | | N | N | N |
| Group 1 | Rabipur® | N/A | 10 | 10 | 10 |
| Group 2* | CV7202 | 5 µg mRNA | 10 | N/A | N/A |
| Group 3 • Group 3a** | | 1 µg mRNA | 16 | | 8 |
| Group 4 • Group 4a** | | 2 µg mRNA | 16 | | 8 |
| Total CV7202 | | | 42 | | 16 |

* Note that enrolment in Group 2 was already completed at the time this protocol amendment was issued.

** 'a' groups are a subset consisting of 8 subjects of Groups 3 and 4 scheduled to receive a first dose on Day 1 and a second dose on Day 29.

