8.5 Method of Trial Vaccine Assignment

This trial is non-randomized. Eight vaccinated subjects in Groups 3 and 4 will receive two doses of CV7202 and the remaining 8 subjects in these groups will receive one dose of CV7202.

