10.2 Populations for Analyses

Safety set: This is the subset of subjects, who have received at least one dose of the candidate rabies mRNA vaccine CV7202 or the active control Rabipur® and for whom any post-Day 1 safety data are available. The statement that a subject had no AEs (on the Adverse Event eCRF) constitutes a valid safety assessment. The analysis of safety will be performed on this population.

Full-analysis (FA) set: This is the subset of the Safety Set with subjects who have the baseline sample and at least one additional blood sample available for VNT analysis. This analysis set is the primary analysis set for all immunogenicity objectives.

Per protocol (PP) set: This is defined as a subset of the FA set as follows:

1. PP1 = Subjects enrolled in Group 1 (Rabipur®) and Groups 2 to 4 who have received at least 1 administration of the trial product (including those to be selected for the second vaccination), have completed the Day 57 visit and for whom baseline through Day 57 immunological results (at least rabies VNTs) are available.
2. PP2 = Defined as a subset of PP1 comprised of subjects who have received two administrations of the trial product, have completed the Day 91 visit and for whom baseline through Day 91 immunological results (at least rabies VNTs) are available.

Any subject for whom substantive protocol deviations are documented will be excluded from the PP set. The following pre-defined major protocol deviations will lead to the exclusion from the PP set:

- Any deviation of the Inclusion/Exclusion criteria.
- Any trial subject that requires therapy listed as an exclusion criterion in section 6.2.
- Any trial subject that has not received the trial product on the scheduled date.
- Any trial subject for whom the immunological sample has been taken outside of the planned visit window.
- Pre-existing RABV-G specific immune response.

Further subgroup analyses may be defined and specified in the statistical analysis plan (SAP).

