4. TRIAL DESIGN AND PLAN

This is a non-randomized, open label, controlled, dose-escalation, phase I clinical trial to evaluate the safety, reactogenicity, and immunogenicity of 1 or 2 i.m. administrations of candidate rabies messenger ribonucleic acid (mRNA) vaccine CV7202 in healthy adult subjects.

Subjects will be enrolled in 2 trial sites, 1 in Germany, 1 in Belgium.

Approximately 52 subjects will be enrolled sequentially in up to 4 trial groups to receive either a dose of CV7202 containing different mRNA content or Rabipur. In a first CV7202 group, 10 subjects have received a dose containing 5 µg mRNA. A dose of 1 or 2 µg mRNA will be administered to 2 additional groups of 16 subjects each, of whom 8 in each group will be administered a second dose 28 days later. A control group of 10 subjects will receive 3 doses of the licensed vaccine Rabipur according to the manufacturer's recommendations. Safety and immunogenicity assessments will be made up to 2 years following the last dose administration.

Specified safety data will be reviewed by an internal safety review committee and a data safety monitoring board on a pre-defined schedule. At each planned safety review, safety data will be reviewed, and a GO/NO GO decision made accordingly for enrollment of further subjects and administration of subsequent doses.

Enrollment will be staggered in Groups 2 to 4 to ensure the safety of the participating subjects. Enrollment into Group 1 (1.0 ml Rabipur) will not be staggered, since the clinical safety of Rabipur is well established.

Subjects will be enrolled at pre-screening (Day -90 to -1) to receive either CV7202 starting on Day 1 as 1 dose or 2 doses (at least 28 days apart), or 3 doses of control vaccine (Rabipur). Follow-up for safety and immunogenicity is planned up to 24 months after the last dose; therefore, the expected duration of participation for each subject is approximately 24 months after the last dose.

Please refer to protocol section 5 for more details of trial design, protocol section 6 for trial population and protocol section 7 for discontinuation/withdrawal criteria.

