12. CHANGES TO PROTOCOL-SPECIFIED ANALYSES

The protocol defines 2 PP sets as subsets of the FA set. Due to the small number of subjects per treatment group, it was decided that no per-protocol sets will be defined and used for analysis.

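### Does tabulating by the regimen received sort subjects into the one- and two-dose columns by how well they tolerated Dose 1?

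*SAP*

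**What the plan says.** **How the regimen is set.** Protocol 8.5 gives the split and nothing more: "Eight vaccinated subjects in Groups 3 and 4 will receive two doses of CV7202 and the remaining 8 subjects" in those groups get one dose. Protocol 5.2 describes subjects enrolled "to receive either CV7202 starting Day 1 as 1 dose or 2 doses (at least 28 days apart", and SAP 4 repeats this almost word for word. The footnote to Table 8.1 in Protocol 8.4 defines the 'a' groups as subjects "scheduled to receive a first dose on Day 1 and a second dose on Day 29". These passages read as a regimen fixed in advance. The PP1 definition in Protocol 10.2 reads differently: "including those to be selected for the second vaccination". SAP 12 removes that set: "it was decided that no per-protocol sets will be defined and used for analysis".

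**Who may not get Dose 2.** Protocol 5.1.2 says "Subjects must not receive a second dose of CV7202 in the event of" an allergic or anaphylactic reaction, a related SAE, or a related grade 3 AE outside the listed transient exceptions. Such subjects are encouraged to stay in follow-up.

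**How the data are tabulated.** SAP 7 reports that second doses went to 8 of the 16 subjects in each group, one after another at the sites. It therefore does not separate planned from actual regimen: "all analyses will be based on the actually received vaccination group and dose regimen". No table or listing shell carries a designated regimen.

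**The concern.** Read together, Protocol 5.1.2 and SAP 7 mean that a subject who reacted badly to Dose 1 can be counted only under 1x1 µg or 1x2 µg. If anyone was barred, the 2x columns hold only subjects who tolerated Dose 1, while the 1x columns hold a mixture.

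Choosing the number of doses is a stated purpose of the trial (Protocol 1, Rationale). Tables 14.2.1.2, 14.2.1.4, 14.3.1.3.2, 14.3.5.2 and 14.3.5.4 set 1x beside 2x. The sharpest example is 14.3.5.4, which shows injection-site grades after Dose 1 (V3 and V4) split by later regimen. With 8 per column, one barred subject is 1/8 = 12.5 percentage points of the 1x column and cannot appear under 2x. Without a record of intent, a reader could not tell tolerance selection from a regimen effect.

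**Working it through.** **1. The plan's own counts.** Table 8.1: 10 + 16 + 16 = 42 CV7202 subjects on Day 1, and 8 + 8 = 16 on Day 29. With 10 on Rabipur the total is 52. At the second interim analysis (SAP 6.4) the CV7202 groups stood at 16, 16 and 10, as planned. Groups 3 and 4 had not been topped up.

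**2. Can received differ from designated?** Suppose 8 subjects per group were designated before Dose 1. If one was barred and the slot stayed empty, 7 would have had two doses and 9 one dose. SAP 7 reports 8 of 16. With no refilling, every two-dose recipient is a designated subject; there are 8 of each, so the two sets are identical. They differ only if a one-dose subject was moved into a vacated slot. No passage provides for this, and Protocol 7.2 rules out replacing discontinued subjects except for early dropouts among the first four of each group.

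**3. How often the question would arise.** The documents give no barring rate. I assume r = 1%, 2%, 5% or 10%.

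| Quantity | Formula | 1% | 2% | 5% | 10% |
|---|---|---|---|---|---|
| At least 1 of 8 designated barred | 1 − (1 − r)^8 | 0.077 | 0.149 | 0.337 | 0.570 |
| At least 1 of 16 barred | 1 − (1 − r)^16 | 0.149 | 0.276 | 0.560 | 0.815 |
| Expected barred share of the 1x column if the 8 are chosen after Dose 1 | 16r/8 | 0.02 | 0.04 | 0.10 | 0.20 |

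The first row describes how often a slot would fall vacant. It leads to misclassification only if the slot was then refilled. The third row applies only if selection came after Dose 1.

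**4. Effect on titres if selection came after Dose 1.** Assume log10 SD 0.5 and a correlation ρ between reactogenicity and titre, and take the barred subjects as the top fraction r on reactogenicity. The 1x/2x GMT ratio before Dose 2 (truth 1.0) is 10^(ρ × 0.5 × 2r × (m_b − m_t)). Here m_b = φ(c)/r, m_t = −φ(c)/(1 − r), and c is the normal (1 − r) quantile.

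For r = 10% and ρ = 0.4: φ(c) = 0.1755, m_b = 1.755, m_t = −0.195, and 10^(0.4 × 0.5 × 0.20 × 1.950) = 10^0.078 = 1.20.

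| ρ | 1% | 2% | 5% | 10% |
|---|---|---|---|---|
| 0 | 1.00 | 1.00 | 1.00 | 1.00 |
| 0.2 | 1.01 | 1.02 | 1.05 | 1.09 |
| 0.4 | 1.02 | 1.05 | 1.11 | 1.20 |

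The 95% interval for a ratio of two GMTs with 8 per column is 10^(2.145 × 0.5 × √(1/8 + 1/8)) = 10^(2.145 × 0.25) = 3.44-fold each way. If a slot had been vacated and refilled, the ratio would be 1.09 to 1.13 at ρ = 0.2 and 1.19 to 1.28 at ρ = 0.4, still well inside that interval.

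**5. Effect on safety outputs.** The Dose 1 solicited tables, the 28-day unsolicited tables after Dose 1 and table 14.3.5.3 pool all 16 subjects at a dose level, so regimen labels do not touch them. In 14.3.5.4 the V3 and V4 rows compare subjects who had received the same treatment up to that point. They say nothing about one dose against two. The exact 95% interval for 1 of 8 runs from 0.3% to 52.7%, so a one-subject shift is well within noise.

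**6. Would a barred subject be visible?** Protocol 7.1 has the main reason for stopping CV7202 entered in the eCRF. Protocol 9.2 collects AEs leading to vaccine withdrawal without restricting them to unsolicited events, and SAP 11.2.2 has the investigator enter them in the eCRF. Listing 16.2.5 shows each dose given, and protocol deviations are listed.

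**The case for a change.** The strongest reply is that none of this proves the columns are clean. Giving second doses one after another describes order, not a rule for choosing. The bar on replacement in Protocol 7.2 may concern new enrolment only, so a slot could have been refilled from within the group. Table 8.1 defines the 'a' groups by schedule and Protocol 10.3.1 asks for them as separate columns. SAP 7 fills those columns by receipt, and SAP 12 does not list that as a change. The records are also imperfect. The discontinued-vaccination rows and listing 16.2.7.1.4 sit under unsolicited AEs, and SAP 11.2.1 sends a solicited reaction to the AE pages only if it is serious or ongoing on Day 8. The solicited listings have no field for action taken.

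The documentation gap stands: the text does not say how the 8 were chosen, and the passages do not read alike. The step from there to a distorted comparison does not stand. It needs either a refill that no passage describes or a choice after Dose 1 that rests on a phrase in a dropped set. The Day 8 route is also not the only one, because AEs leading to vaccine withdrawal have their own collection. The heading over those outputs leaves some ambiguity, but not enough to conclude that a barred subject would go unseen.

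Extra tables would add little. Tables by designated regimen would repeat the existing ones if the two regimens coincide. A one-dose column restricted to subjects not barred would need retrospective, unblinded judgement from medical files, using a rule counted in hours. It would remove an expected 8r to 16r subjects from a column of 8: 0.08 to 0.16 at 1%, and 0.8 to 1.6 at 10%.

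**Conclusion.** No change to the plan. Summarising by regimen received is a legitimate choice in a non-randomised, open-label, descriptive phase I trial, and SAP 7 states it openly. There is no randomised contrast to protect. Following the plan as written most likely gives the same tables as an analysis by designated regimen.

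This rests on reading the 8 of 16 in SAP 7 as a count of what happened, and on no vacated slot having been refilled. If instead the 8 were chosen after Dose 1, the estimated distortion is a GMT ratio of 1.00 to 1.20 against an interval of 3.4-fold each way. That range depends on assumed barring rates of 1% to 10%, an SD of 0.5 and correlations of 0 to 0.4. Selection on tolerance is possible, but nothing in the documents shows that it occurred.

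What is left is missing detail. The trial report can state how and when the 8 were chosen and whether anyone was barred under Protocol 5.1.2, using records the sponsor already collects. An analyst would look further only if a subject's intended and received regimens turned out to differ.
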